- 2) I have received an explanation from the gene therapy institution regarding the necessary measures to ensure the safety of gene therapy.
- 3) Even if the consenting person agrees to the above matters, consent can be withdrawn at any time before the treatment begins.
- 4) The gene therapy institution is obligated to take necessary measures to protect the personal information of the consenting person.

I hereby declare that my consent to the above matters is given voluntarily

Signature

Subject :

Informed consent counselor :

[Appendix 5] WHO toxicity scale

WHO recommendations for grading of acute and subacute toxic effects

	Grade 0	Grade 1	Grade 2	Grade 3	Grade 4
1. Hematologic (adults)					
Hemoglobin g/100 mL	≥ 11.0	9.5 - 10.9	8.0 – 9.4	6.5 – 7.9	< 6.5
Leukocyte 1000/cmm	≥ 4.0	3.0 – 3.9	2.0 – 2.9	1.0 – 1.9	< 1.0
Granulocyte 1000/cmm	≥ 2.0	1.5 – 1.9	1.0 – 1.4	0.5 – 0.9	< 0.5
Platelets 1000/cmm	≥ 100	75 – 99	50 – 74	25 – 49	< 25
Hemorrhage	None	Petechiae	Mild blood loss	Gross blood loss	Debilitating blood loss
2. Gastrointestinal					
Bilirubin	≤ 1.25 x N*	1.26 – 2.5 x N	2.6 – 5 x N	5.1 – 10 x N	> 10 x N
SGOT/SGPT	≤ 1.25 x N	1.26 – 2.5 x N	2.6 – 5 x N	5.1 – 10 x N	> 10 x N
Alkaline phosphatase	≤ 1.25 x N	1.26 – 2.5 x N	2.6 – 5 x N	5.1 – 10 x N	> 10 x N
Oral	No change	Soreness/erythema	Erythema, ulcers; can eat solids	Ulcers; requires liquid diet only	Alimentation not possible
Nausea/vomiting	None	Nausea	Transient	Vomiting requiring extra therapy	Intractable vomiting
Diarrhea	None	Transient < 2 days	Tolerable but > 2 days	Intolerable requiring therapy	Hemorrhagic dehydration
3. Renal, bladder					
BUN or blood urea	≤ 1.25 x N	1.26 – 2.5 x N	2.6 – 5 x N	5.1 – 10 x N	> 10 x N
Blood creatinine	≤ 1.25 x N	1.26 – 2.5 x N	2.6 – 5 x N	5.1 – 10 x N	> 10 x N
Proteinuria	None	1+, < 0.3g/100mL	2-3+, 0.3-1.0g/mL	4+, > 1.0g/100mL	Nephrotic syndrome
Hematuria	None	Microscopic	Gross	Gross + clots	Obstructive uropathy
4. Pulmonary	None	Mild symptoms	Exertional dyspnea	Dyspnea at rest	Complete bed rest required
5. Fever-drug	None	Fever < 38°C	Fever 38°C - 40°C	Fever > 40°C	Fever with hypotension
6. Allergic	None	Edema	Bronchospasm; no parenteral therapy needed	Bronchospasm; parenteral therapy needed	Anaphylaxis
7. Cutaneous	None	Erythema	Dry, desquamation, vesication, pruritus	Mist, desquamation, ulceration	Exfoliative dermatitis; necrosis requiring, surgical intervention

8. Hair	None	Minimal hair loss	Moderate, patchy alopecia	Complete alopecia but reversible	Nonreversible alopecia
9. Infection (specify site)	None	Minor infection	Moderate infection	Major infection	Major infection with hypotension
10. Cardiac					
Rhythm	No change	Sinus tachycardia > 110 at rest	Unifocal PVC, arterial arrhythmia	Multifocal PVC	Ventricular tachycardia
Function	No change	Asymptomatic but abnormal cardiac sign	Transient symptomatic dysfunction; no therapy required	Symptomatic dysfunction responsive to therapy	Symptomatic dysfunction nonresponsive to therapy
Pericarditis	No change	Asymptomatic effusion	Symptomatic; no tap required	Tamponade; tap required	Tamponade; surgery required
11. Neurologic					
State of consciousness	Alter	Transient lethargy	Somnolent < 50% of waking hours	Somnolent > 50% of waking hours	Coma
Peripheral	None	Paresthesias and/or decreased tendon reflexes	Severe paresthesias and/or mild weakness	Intolerable paresthesias and/or marked motor loss	Paralysis
Constipation**	None	Mild	Moderate	Abdominal distention	Distention and vomiting
12. Pain***	None	Mild	Moderate	Severe	Intractable

These guidelines resulted from two international meetings organized on the initiative of the World Health Organization, as published by Miller AB, et al: Cancer 1981; 47: 207

*N, upper limit of normal

** Constipation does not include constipation resulting from narcotics.

*** Only treatment-related pain is considered, not disease-related pain. The use of narcotics may be helpful in grading pain, depending upon the tolerance level of the patient.

[Appendix 6] JNC VII Guide to Prevention and Treatment of Hypertension

Recommendations

Classification and management of blood pressure for adults aged 18 years or older

BP classification	Systolic BP* (mmHg)	Diastolic BP* (mmHg)	Lifestyle modification	Initial drug therapy	
				Without compelling indications	With compelling indications
Normal	Less than 120	Less than 80	Encourage	No antihypertensive drug indicated	Drug(s) for compelling indications. ‡
Prehypertension	120 – 139	80 – 89	Yes		
Stage 1 hypertension	140 – 159	90 – 99	Yes	Thiazide-type diuretics for most. May consider ACEI, ARB, BB, CCB, or combination.	Drug(s) for the compelling indications. ‡ Other antihypertensive drugs (diuretics, ACEI, ARB, BB, CCB) as needed.
Stage 2 hypertension	160 and above	100 and above	Yes	Two-drug combination for most† (usually thiazide-type diuretic and ACEI or ARB or BB or CCB).	

Drug abbreviations: ACEI-angiotensin converting enzyme inhibitor;ARB-angiotensin receptor blocker;BB-beta blocker;CCB-calcium channel blocker.

* Treatment determined by highest BP category.

† Initial combined therapy should be used cautiously in those at risk for orthostatic hypotension.

‡ Treat patients with chronic kidney disease or diabetes to BP goal of <130/80 mmHg.

[Appendix 7] Killip class

Class	Definition
Killip class I	individuals with no clinical signs of heart failure
Killip class II	individuals with rales in the lungs, an S3 gallop, and elevated jugular venous pressure*
Killip class III	individuals with frank pulmonary edema.
Killip class IV	individuals in cardiogenic shock

* Reference: Drazner MH, Rame JE, Stevenson LW, Dries DL. Prognostic importance of elevated jugular venous pressure and a third heart sound in patients with heart failure. *N Engl J Med.* 2001 Aug 23;345(8):574-81

[Appendix 8] Canadian cardiovascular society (CCS) class

Canadian cardiovascular society functional classification of angina pectoris

Class	Definition
Class I	Ordinary physical activity (eg. Walking and climbing stairs) dose not cause angina; angina occurs with strenuous, rapid, or prolonged exertion at work or recreation.
Class II	Slight limitation of ordinary activity; angina occurs on walking or climbing stairs rapidly; walking uphill; walking or stair climbing after meals, in cold, in wind, or under emotional stress; or only during the few hours after awakening; when walking>2 blocks on level ground; or when climbing more than 1 flight of stairs at a normal pace and in normal conditions.
Class III	Marked limitation of ordinary physical activity; angina occurs on walking 1 to 2 blocks on level ground or climbing 1 flight of stairs at a normal pace in normal conditions.
Class IV	Inability to perform any physical activity without discomfort; anginal symptom may be present at rest

Adapted from Goldman L, Hashimoto B, Cook EF, Loscalzo A. Comparative reproducibility and validity of systems for assessing cardiovascular functional class; advantages of new specific activity scale Circulation. 1981;64:1227~1234.

[Appendix 9] New York heart association (NYHA) functional classification

A functional and therapeutic classification for prescription of physical activity for cardiac patients.

Class	Definition
Class I	Patients with cardiac disease, but without resulting limitation of physical activity. Ordinary physical activity dose not cause undue fatigue, palpitation, dyspnea, or anginal pain..
Class II	Patients with cardiac disease resulting in slight limitation of physical activity. They are comfortable at rest. Ordinary physical activity results in fatigue, palpitation, dyspnea, or anginal pain.
Class III	Patients with marked limitation of physical activity. They are comfortable at rest. Less than ordinary activity cause fatigue, palpitation, dyspnea, or anginal pain.
Class IV	Patients with cardiac disease resulting in inability to carry on any physical activity without discomfort. Symptoms of heart failure or of the anginal syndrome may be present even at rest. If any physical activity is undertaken, discomfort is increased.

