	
5) revascularization
 
5) Safety evaluation of intramuscular injection of VM202RY: Evaluation for persistent bleeding, arrhythmia, and other complications
 
Secondary endpoint:
 
- Efficacy
1) Cardiac function: Left ventricular ejection fraction and regional cardiac function by cardiac MRI, myocardial SPECT, and echocardiography2) Viable myocardium: Cardiac MRI (myocardial thickness of the intramuscular injection area, extent of gadolinium late enhancement, and exercise intensity of the region)3) Changes in myocardial ischemic area: Myocardial SPECT (blood flow changes in the intramuscular injection area at rest and under load)- HGF concentration in blood
1) Changes in plasma HGF concentration after VM202RY administration- Anti-HGF antibody production by VM202RY administration
1) Comparison of ELISA results using serum from subjects administered with VM202RY
Statistics	
Primary endpoint
 
- Safety evaluation
1) Dose limiting toxicity Dose-limiting toxicity is assessed 4 weeks after administration of the investigational product, VM202RY and refers to cases where toxicity of Grade 3 or higher occurs based on the WHO Toxicity scale or severe adverse reactions occur according to the Spilker classification system. However, adverse reactions accompanying coronary artery bypass grafting (CABG) are excluded.2) Tolerated dose The subjects are registered sequentially from Step 1 as follows to confirm the tolerance capacity.
1. After enrolling 3 subjects in the first dose group and evaluating DLT 4 weeks after administration to the third subject,
1-1. No DLT occurred in any of the 3 patients (0/3) → 3 patients enrolled in the second dose group (A)1-2. DLT occurred in 1 out of 3 patients (1/3) → Additional registration of 3 patients with the same dose
1-2-1. No DLT occurrence for all 3 added (1/6) → 3 people registered in the second dose group (A)1-2-2. 1 out of 3 additional patients developed DLT (2/6) → Stop increasing dose

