2. POD#1 DAY: If there is no bleeding and the hemodynamic status is stable, the ventilator is removed. Intravenous vasodilators are switched to oral medications. Continuous monitoring of systemic and pulmonary arterial pressure and ECG continues. Once hemodynamic stability is confirmed, the patient is transferred to the general ward and monitored with a 24-hour ECG.
3. POD#2 DAY: Under 24-hour ECG monitoring, the patient begins light physical activity in the ward. Chest tubes are removed if daily drainage is less than 1cc per kg of body weight.
4. POD#3 ~ 6 DAY: While continuing 24-hour ECG monitoring, physical activity is gradually increased in the ward. The patient is observed for allergic reactions possibly related to gene therapy, such as skin rashes, angioedema, or bronchospasm.
5. POD#7 DAY: Holter monitoring is performed, and transthoracic echocardiography is conducted to evaluate cardiac function. If no abnormalities are found, discharge is considered.

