17.3.3 Safety evaluation methods and criteria

1) DLT (Dose Limiting Toxicity)

Dose Limiting Toxicity (DLT) is evaluated from the first day of investigational drug administration up to 4 weeks post-administration. DLT is defined as adverse reactions of Grade 3 or higher according to the WHO Toxicity Scale, or severe adverse reactions classified as Grade 3 by Spilker's three-tier classification method, excluding adverse reactions associated with coronary artery bypass grafting (CABG).

Adverse reactions specific to CABG caused by the surgery itself are excluded from the DLT evaluation.

1. Blood test findings (in cases recovered without complications)
 - (1) Hemoglobin: 8-17
 - (2) WBC: 4-25
 - (3) Platelet: 50-550
 - (4) Bilirubin: 0.3-10.6
 - (5) GOT/GPT: 9-125/8-350

- (6) Alk. Phosphatase: 35-180
- (7) BUN/Cr: it depends on the patient's preoperative kidney function
- 2. Reoperation due to bleeding: occurs in 5-10% of cases.
- 3. Fever: A persistent fever above 39°C is rare unless pulmonary complications or infections occur. Therefore, a fever above 39°C lasting more than 24 hours is considered outside the range of common complications.
- 4. Infection: Mediastinitis occurs in 2-3% of cases.
- 5. Arrhythmia: Atrial fibrillation occurs in 20-30% of cases. Transient premature ventricular contractions (PVCs) are common, but the occurrence of multifocal PVCs is considered abnormal. Ventricular tachycardia and fibrillation may occur due to postoperative bleeding, myocardial dysfunction, or reperfusion injury in chronically ischemic areas. If these are clearly related to surgery, such as bleeding from the graft or cardiac tamponade, they are considered surgical complications. However, unexplained ventricular arrhythmias can occasionally occur. Recurrent ventricular arrhythmias are uncommon in patients discharged after surgery. If the patient had recurrent ventricular arrhythmias before surgery with a consistent pattern and interval, these are not considered caused by gene therapy, but follow-up with Holter monitoring is needed to track any changes.

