18.1 Definition of adverse events

An adverse event is defined as the occurrence or worsening of any of the following:

- 1) All symptoms and signs not related to the primary diagnosis, or symptoms and signs that are aggravated and related to the primary diagnosis
- 2) Clinically significant abnormalities in laboratory test results
- 3) Abnormal findings from physical examinations

These events must be recorded in the CRF even if they are not considered related to the investigational product (i.e., "possibly related" events should be recorded).

The investigator should assess adverse events according to the WHO Toxicity Scale. If the WHO scale is not applicable, the severity of adverse events should be evaluated using Spilker's three-grade classification system.

Grade	Criteria
Mild	When no treatment is required, and the subject's normal daily life (functions) is not significantly impaired
Moderate	When the subject's normal daily life (functions) is significantly impaired, treatment may be required, and recovery occurs after treatment
Severe	When a severe adverse reaction requires intensive medical intervention and leads to lasting aftereffects, or in cases of life-threatening adverse events

The investigator shall evaluate the causality between the adverse event and the investigational product based on the following criteria:

- 1) Definitely related
 - There is evidence that the investigational product was administered.
 - The temporal relationship between administration and the adverse event is appropriate.
 - The adverse event is more likely explained by administration of the investigational product than by any other cause.
 - The adverse event resolves upon discontinuation of the investigational product.
 - The adverse event reappears upon rechallenge (if performed).
 - The adverse event is consistent with known information about this product or products of the same class.
- 2) Probably related
 - There is evidence that the investigational product was administered.
 - The temporal relationship between administration and the adverse event is appropriate.
 - The adverse event is more likely explained by administration of the investigational product than by other possible causes.
 - The adverse event resolves upon discontinuation of the investigational product.
- 3) Possibly related
 - There is evidence that the investigational product was administered.

- The temporal relationship between administration and the adverse event is appropriate.

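### 18.1 makes the Spilker scale a fallback while 17.3.3 and the synopsis make it a full alternative, so a life-threatening event graded low on the WHO scale may be missed as a DLT

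*Combined protocol and SAP*

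**What the plan says.** The synopsis (Statistics, dose limiting toxicity) counts a DLT where "toxicity of Grade 3 or higher occurs based on the WHO Toxicity scale or severe adverse reactions occur according to the Spilker classification system". Section 17.3.3, item 1, has the same two-part structure: WHO Grade 3 or higher, or "severe adverse reactions classified as Grade 3 by" the Spilker three-tier scheme. In both places the two parts are joined by a plain *or*, and reactions to the bypass surgery are excluded.

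Section 18.1 gives the grading instruction. The WHO scale comes first, and then: "If the WHO scale is not applicable, the severity of adverse events should be evaluated using Spilker's three-grade classification system". The Severe class in the 18.1 table ends with "or in cases of life-threatening adverse events".

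In Appendix 5, the Allergic row has edema at Grade 1, bronchospasm without parenteral treatment at Grade 2, "Bronchospasm; parenteral therapy needed" at Grade 3 and anaphylaxis at Grade 4. The word angioedema does not appear on the scale. Section 14.2, for postoperative days 3 to 6, says: "The patient is observed for allergic reactions possibly related to gene therapy, such as skin rashes, angioedema, or bronchospasm".

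**The concern.** The DLT definition needs two grades to be available, but the grading instruction may supply only one. Where a WHO row exists, an investigator following 18.1 has no call to assign a Spilker grade. A life-threatening event that sits in a low WHO cell is then a DLT by the words of 17.3.3 and a low-grade event by the procedure of 18.1. Angioedema is a foreseen event of this kind, and its row has no cell that separates mild from dangerous edema.

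DLT is the first item of the primary endpoint and the input to every escalation step. The grade also controls a second safeguard: 18.1 requires causality to be judged by two or more investigators for a DLT or for an unexpected event of Grade 3 or above. An event left at Grade 1 would not trigger that review.

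**Working it through.** **1. The plan's own figures.** Three dose groups of 3 give 3 × 3 = 9 planned subjects. Three groups expanded to 6 give 3 × 6 = 18 at most. Both match 11.4, and neither is in dispute.

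**2. One event under the two texts.** Take angioedema in the first postoperative week that is judged life-threatening, with no other cause clearly identified. It falls inside the 4-week DLT window. The allergic exclusion in 17.3.3 does not remove it, because that exclusion needs a clearly identified cause.

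| Step | 17.3.3 and synopsis | 18.1 taken as governing |
|---|---|---|
| WHO grade, Allergic row | 1 | 1 |
| Spilker grade | Severe | none called for, since a WHO row exists |
| Severity condition for DLT | met | not met |

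The later part of 17.3.3, on surgical reactions by WHO item, restates the dose-limiting threshold by WHO grade alone. It therefore does not settle which column applies.

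**3. Where the two texts agree.** The same event counts under either column if it brings "Dyspnea at rest" (Pulmonary row, Grade 3) or is part of anaphylaxis (Allergic row, Grade 4). It also counts if the investigator decides that the edema cell does not fit angioedema and therefore uses Spilker under 18.1 itself. What remains is an event graded solely on a low WHO cell, with 18.1 read as the controlling text.

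**4. What one uncounted event changes (17.3.3, item 2).**
- 1/3 becomes 0/3: the next dose opens, instead of 3 more subjects at the same dose.
- 2/3 becomes 1/3: the group is expanded, instead of escalation stopping.
- 2/6 becomes 1/6: the next dose opens, instead of escalation stopping. In the third group, the tolerated dose is read as C instead of B.

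**5. Illustration only.** The documents give no rate for such events. Let q be the per-subject rate of events in the gap and o the rate of all other DLTs. Both are assumptions, and the two are taken as independent. The combined rate is p = 1 − (1 − o)(1 − q). A dose is passed on 0/3, or on 1/3 followed by 0/3:

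P(pass) = (1 − p)³ + 3p(1 − p)² × (1 − p)³ = (1 − p)³ + 3p(1 − p)⁵.

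For example, with o = 0 and q = 0.10: 0.729 + 0.3 × 0.59049 = 0.906. If gap events are not counted, p = o.

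| q | o = 0: counted / not counted | o = 0.10: counted / not counted |
|---|---|---|
| 0.05 | 0.97 / 1.00 | 0.82 / 0.91 |
| 0.10 | 0.91 / 1.00 | 0.73 / 0.91 |
| 0.20 | 0.71 / 1.00 | 0.54 / 0.91 |
| 0.33 | 0.43 / 1.00 | 0.31 / 0.91 |

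The shift is small if such events are rare and large only if they are common. The table shows how sensitive the rule is to classification; it does not forecast this trial.

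**The case against.** A reader might infer that dangerous angioedema can never become a DLT, whatever airway support it needs. The documents do not support that. The DLT definition appears twice, each time with an unconditional *or*, and it is the specific rule, whereas 18.1 is the general section on adverse events. Section 18.1 names a case for Spilker but does not forbid its use elsewhere. Angioedema that threatens the airway would ordinarily cause breathlessness at rest, and 17.3.3 excludes only those pulmonary findings that come from reduced cardiac function. All of this stands, and it confines the point to a conflict between sections.

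It does not remove the conflict. Each route depends on an individual judgement about which row, or which section, controls. Breathlessness may also be hard to report on the day of surgery, when 14.2 has the patient on a ventilator.

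It can also be said that the event would not go unseen, since a life-threatening event is serious under 18.3 and is reported at once under 18.4. That is true, but seriousness is not among the criteria for discontinuing escalation in 13.4.6.

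Finally, the earlier HGF gene trial described in 7.2 saw no allergic or anaphylactic reaction in six patients. This is the only human allergy evidence in the documents, and it is compatible with a low rate. It excludes little, however: with 0 of 6, the one-sided 95% upper limit is 1 − 0.05^(1/6) = 0.39, and that trial treated limbs with a different plasmid.

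**Conclusion.** The conflict is real and limited. The definition in 17.3.3 and the synopsis gives the Spilker scale equal standing; 18.1 gives it a fallback role. If 18.1 is followed, a life-threatening event graded solely on a low WHO cell may be missed as a DLT.

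The certain part of its size is structural: in groups of three or six, one such event moves the decision by one step, as listed above. How often that would happen cannot be derived from the documents. The conclusion rests on two assumptions: that investigators grade by 18.1, and that the event meets no other WHO row at Grade 3 or above. Sample size does not depend on it. The point deserves correction because it concerns how the first primary endpoint is classified and costs almost nothing to settle.

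**What to change.** Reconcile 18.1 with 17.3.3 and the synopsis. To make the plan's own *or* workable, add to 18.1 that, for the DLT assessment, a Spilker grade is recorded for each adverse event in addition to any WHO grade. State there too that the severity condition is met when either scale reaches the level already given in 17.3.3. The surgical exclusions, the escalation counts and the WHO scale itself stay as they are.

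The cost is a short addition to 18.1 and one extra CRF field per event. The small downside is that a few more events may be counted as DLTs.
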